**Figure 2: Implementation of Mood CCM across Health Plan, Practices, and Patients**

clinician who treats their mood disorder (i.e., prescribes psychotropic medications). Comorbidities will be ascertained from Aetna eTUMS chart reviews conducted by the RAs.

program evaluation, and will be blinded to randomization assignment. (S)he will be trained by Aetna on their well-established call implementation program across time zones (**Section C.5.c**) and by study investigators in human subjects risk reduction procedures used in prior studies (8, 50) that will minimize risk while not compromising study internal validity (8). The initial assessment (described below) will include a brief survey baseline factors, including demographics, employment, whether they were the Aetna enrollee or a family member, and primary

**C.5.c. Existing Aetna Infrastructure Used in this Study.** The following components are of specific relevance:

1. The registry/database consists of four main components and will be used to identify potentially eligible patients as well as ascertain utilization and other outcomes data (see variable descriptions below). The Electronic Total Utilization Management System (**eTUMS**), a proprietary care management tool is populated by

claims data augmented by customizable care manager input; major claims events, such as hospitalization, result in automatic care manager notification. The **pharmacy claims database** accrues prescription claims daily, including drug and dose, and is downloaded to eTUMS on a weekly basis. **Laboratory claims data** are similarly downloaded on a monthly basis; laboratory reports contain the name of the test, while reports from larger laboratories also provide results. Thus these registries will provide the data necessary to measure guideline-concordant care (e.g., non-filling of mood disorder prescriptions, non-completion of cardiometabolic laboratory tests). The fourth component, **Aetna claims data**, includes use and cost data for Aim 3.

**2. The Aetna care management infrastructure is substantial and stable.** The masters level Aetna care managers who participated in the pilot will serve as the CCM care managers. They have a minimum of 5 years of care management experience with Aetna, providing short-term or ongoing care management for an average of 300 beneficiaries per year across multiple time zones and patient schedules.

**Care manager coverage across time zones:** All Aetna care managers function in teams with supervisory care manager and medical oversight. They also work staggered hours (e.g., covering 9am-midnight ET M-F, 10-6pm Sat) in order to make patient calls across different time zones. Biweekly 1:1 supervisor meetings and monthly team meetings provide support and training. Quality is monitored via audit tools that assess both calls and documentation three times per month. Regular Medical Director Rounds are supplemented by reviews when claims or other data indicate that the beneficiary is not doing well.

**CM and study staff handling of suicide risk/adverse events:** Imminent risk (suicidal or assaultive ideation, significant medication toxicity) are managed via protocols used in prior studies (8, 50, 52). In the pilot study (Section C.3), care managers identified 4 out of 457 who had suicidal ideation and, through established protocols, alerted the provider and arranged emergency evaluation; no suicide attempts occurred during the pilot study. Moreover, CCMs have been shown to reduce suicide (94). Study staff (both University of Michigan and Aetna) will be trained to identify and address suicidal ideation in patients. If the patient articulates thoughts of death or suicidal ideation, the study team member will ask the patient to elaborate on recent suicidal behavior (i.e., ask if he or she has an active plan). Follow-up regarding the situation will be based on the patient's responses and whether the study team member perceives that the patient is in immediate danger (e.g., active plan verbalized). Endorsement of the suicidal thoughts on the survey will also serve as an emergent/urgent situation. The study team member will then ask whether there is another individual with the patient (if over the phone), and will remain on the phone while instructing the other individual to get help. If no one else is present with the patient, the team member direct the patient to his/her local emergency room or, refer to a national suicide hotline that can do further assessment and planning, so the patient can get immediate help. Adverse event reporting is outlined further in the data safety monitoring plan. We will have a adverse events and serious adverse events management plan for this project, as due to the nature of this population, fairly frequent visits to the emergency room that do not require hospitalization and hospitalizations due to their mood disorder exacerbation are to be expected. All adverse events encountered by both University of Michigan and Aetna staff will be reported to the UM IRB according to our management plan (see Data Safety Monitoring Plan document).

**C.5.d. Interventions: EC and CCM.** The **education control (EC) condition** consists of a self-guided workbook mailed to patients developed by study investigators (95) along with standard care from the practice, but none of the CCM components from the plan-level CM.

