**Table 4: Mood Disorders CCM Core Elements: Life Goals Collaborative Care**

CCM Core Element 1: Life Goals Skills Management Enhancement	10 weekly 30-min telephonic sessions utilizing the web-based Life Goals program (52, 95) 
 
• Core modules cover management of depressive and manic symptoms
 
• Additional web modules utilized as clinically indicated (e.g., wellness, foods and moods, exercise, substance use, anxiety, psychosis, anger/irritability, metabolic risk)
 

CCM Core Element 2: Access / Continuity Parameters for Care Manager	12 monthly patient telephone contacts for 1 year (in addition to the skills management training above) to trouble-shoot self-management issues and summarize clinical status

	
Scheduled and Ad Hoc Clinical Assessments and Registry Data Utilization
 
 
• Ad hoc contacts at either care manager or participant initiation based on clinical or other concerns, including response to participants within one business day.
 
• “In-reach” to treating clinicians for hospitalization, ER visits, or specialty consultation
 
• Communication of clinical assessment data to mental health provider
 
• Collaboration with family as permitted
 
• Resource referral as needed
 

CCM Core Element 3: Provider Decision Support via Depression and Bipolar Disorder Clinical Practice Guidelines(96, 97)
	
Provider contacts; care manager elicits preference for mode of communication with provider (e.g., call, email, fax)
 
 
• Same content as clinic-based CCM
 
• Guidelines based on AHRQ depression in primary care and APA bipolar guidelines
 
• Will alert provider that his/her patient is receiving Life Goals and when he/she completes participation
 

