**Patient-level secondary outcomes** include guideline-concordant (quality of) care, hospitalizations, as well as self-reported productivity. These measures are based on recommended indicators from the Accountable Care Organization published rules for performance measures and shared savings (111). We will apply previously established quality measures for mood disorders (98, 111, 112), and cardiometabolic management (113, 114) (Table 5). Quality of care data will be gathered from electronic medical records (eTUMS) and **hospitalization data** will be ascertained from Aetna utilization and claims files at the end of patients' 12 and 24-month participation in two prospectively observed 6-month intervals. Preventable hospitalizations over the 12 and 24-month period will be defined using the AHRQ Ambulatory Care Sensitive Condition (ACSC) definition (115), which identifies conditions for which "good" outpatient care can potentially prevent the need for hospitalization or for which early intervention can prevent complications or more severe disease. We will also assess the probability of psychiatric rehospitalization separately. **Patient-level productivity** over the 24-month period will be assessed in the survey using the Work Limitation Questionnaire(116).

**Patient factors** include CCM engagement ascertained from the patient survey. Engagement is based on the six-item Preference Index for Decision-Making (**API-D**; (117, 118)) which has been used in chronically ill samples to investigate the desire for collaborative care from clinicians. Other patient factors include demographic and clinical information, including co-occurring symptoms (substance use (121, 122), comorbidities (from eTUMS).

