**Aim 3: Utilization, costs, CEA, and business case:** Primary utilization measures of interest, including outpatient services, inpatient (including length of stay), and ER use, and health care costs will be ascertained from Aetna eTUMS electronic record reviews using a standard assessment tool (125). Cost data will be estimated for each inpatient, ER, and outpatient visit using Current Procedural Terminology (CPT) codes. A relative value unit (RVU) weight will allow for the use of the Medicare Fee Schedule to calculate a standardized cost for each service. Costs incurred in different years will be discounted at an annual rate of 3% and adjusted for inflation and discounted to the baseline (first) year of the study. Other costs incurred by the participants including medications, visit co-pays, transportation, and time involved in the CCM will be ascertained from the

patient survey. CCM cost data will be estimated using a time-motion survey developed by study investigators (R01 MH 79994) administered monthly to the CMs and quarterly to providers over a 2-year period, which ascertains time spent on CCM activities, including self-management, phone contacts, and documentation.

**C.5.g. Analyses.** General approach: The principal analyses will be for the primary hypotheses. An intent-to-treat analysis will be performed for all analyses. Bivariate baseline analyses will first be conducted to see if randomization was successful by comparing patient demographics and clinical characteristics (e.g., mental health diagnoses) between randomization groups. If there is a lack of equal distribution across groups, these variables will be added as covariates to analyses or propensity scoring will be used. Baseline characteristics will be compared among those enrolled but dropped out over time to those who remained in the study. Our unit of analysis for patient-level outcomes will be patients nested within practices with an indicator for non-solo practice provider sites (126, 127) and an indicator for patients diagnosis (bipolar vs. unipolar depression).

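### Guideline concordance and Aim 3 utilisation may be scored from eTUMS, whose care-manager entries are likely concentrated in the CCM arm; score both from claims fields only

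*Combined protocol and SAP*

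**What the plan says.** **What eTUMS is.** Section C.5.c describes it as a care-management tool holding "claims data augmented by customizable care manager input". Two claims feeds run into it. The pharmacy database "accrues prescription claims daily, including drug and dose, and is downloaded to eTUMS on a weekly basis", and laboratory claims "are similarly downloaded on a monthly basis; laboratory reports contain the name of the test". The section concludes: "Thus these registries will provide the data necessary to measure guideline-concordant care (e.g., non-filling of mood disorder prescriptions, non-completion of cardiometabolic laboratory tests").

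**Guideline concordance.** Section C.5.f states: "Quality of care data will be gathered from electronic medical records (eTUMS"). Table 5 gives the source as the eTUMS medical record together with claims.

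**Aim 3 utilisation and costs.** The source is named in three ways:
- C.5.c assigns use and cost data for Aim 3 to the claims data, and Table 5 likewise lists claims (with a provider survey).
- The paragraph on utilisation and cost data in C.5.f names eTUMS and the claims databases together.
- The Aim 3 paragraph of C.5.f says that outpatient, inpatient and ER use and health care costs "will be ascertained from Aetna eTUMS electronic record reviews using a standard assessment tool".

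**Hospitalisation as an Aim 1 secondary outcome.** These data "will be ascertained from Aetna utilization and claims files", and Table 5 agrees.

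**Care-manager contact.** Table 4 gives the CCM arm ten weekly sessions and "12 monthly patient telephone contacts for 1 year". Section C.5.d puts medication use, adherence and side effects into the monthly assessment, adds calls after a hospitalisation or ER visit, and has the care manager obtain the provider's planned visits, medications and laboratory tests. EC consists of a mailed workbook plus standard care, without any CCM component.

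**The concern.** A record that mixes claims with notes captures more when someone is writing notes. By design, CCM care managers have far more contact with their patients, and much of what they ask about (medication, laboratory tests, hospital and ER use) falls in the domains later scored as outcomes. A prescription, test or visit known only from a care-manager entry could then be counted for a CCM patient, while the same service in an EC patient goes unseen.

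The two outcomes would be affected differently. Extra capture of treatment and monitoring would raise measured concordance in CCM and so favour CCM. Extra capture of visits would raise CCM utilisation and cost, and so count against CCM in the cost-effectiveness analysis and business case. Neither shift would be a treatment effect, and randomisation does not protect against it because it arises after allocation.

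**Working it through.** **1. Source by outcome**

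| Outcome | Source named | Can care-manager entries reach it? |
|---|---|---|
| PHQ-9, ISS, SF-12 | Patient survey | No |
| Work productivity | Patient survey | No |
| Hospitalisation (Aim 1 secondary) | Utilisation and claims files | No, as written |
| Guideline concordance | eTUMS (C.5.f); eTUMS and claims (Table 5) | Possible; not excluded |
| Aim 3 inpatient, outpatient and ER use, costs | Claims (C.5.c, Table 5); eTUMS and claims (C.5.f); eTUMS record review (C.5.f, Aim 3) | Possible under the last two |

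No section says that care-manager entries count toward an outcome, and none says that they are excluded.

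**2. The plan's own power figure**

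Inputs from C.5.i: two-sided 0.05; concordance 46.5% (CCM) and 27.1% (EC); ICC 0.05; 2 patients per practice; 172 patients per arm; 20% dropout.

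- Design effect = 1 + (2 − 1) × 0.05 = 1.05.
- Effective n per arm = 172 / 1.05 = 163.8. After dropout, 172 × 0.8 = 137.6, and 137.6 / 1.05 = 131.0.
- Rejection probability = Φ[(d − 1.96·SE0)/SE1] + Φ[(−d − 1.96·SE0)/SE1], where d = p1 − p2, SE0 = √[2p̄(1 − p̄)/n], SE1 = √{[p1(1 − p1) + p2(1 − p2)]/n} and p̄ is the mean of p1 and p2.
- For 137.6 per arm: d = 0.194, SE0 = 0.0596, SE1 = 0.0584, first argument 1.32, power 90.7%.
- For 172 per arm: first argument 1.72, power 95.7%.

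The stated power of more than 90% is reproduced.

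**3. Scale of a capture difference**

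The documents give no capture rate, so the following gains are assumptions. Set true concordance to 27.1% in both arms and let care-manager entries add a fixed number of points to the measured rate in CCM.

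Example, 5 points and 137.6 per arm: p1 = 0.321, p2 = 0.271, SE0 = 0.0564, SE1 = 0.0563. The arguments are (0.05 − 1.96 × 0.0564)/0.0563 = −1.08 and −2.85, so the rejection probability is 0.141 + 0.002 = 14.3%.

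| Assumed spurious gain in CCM | 137.6 per arm | 172 per arm |
|---|---|---|
| 0 points | 5.0% | 5.0% |
| 2 points | 6.5% | 6.9% |
| 5 points | 14.3% | 16.8% |
| 10 points | 41.0% | 49.1% |

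The 172 column is shown because outcomes taken from records or claims need not be lost when a patient stops answering the survey.

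The same question can be put as under-capture in EC. With full capture in CCM and 95, 90, 80 or 70% in EC, the spurious difference is 27.1 × (1 − capture) = 1.4, 2.7, 5.4 or 8.1 points. The false-positive rate with 137.6 per arm is then 5.7, 7.9, 17.5 or 34.5%.

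If concordance is scored from pharmacy and laboratory claims alone, care-manager entries add nothing and the rate stays at 5%. No comparable calculation is possible for utilisation, because the documents give no visit rates.

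**The case against.** The strongest reply is that the plan already thinks in claims terms. Immediately after describing eTUMS, C.5.c explains concordance through prescription fills and completed laboratory tests. These arrive through feeds that do not depend on arm, and the Table 5 measures match those feeds. Aim 3 visits are costed from CPT codes and relative value units, which are billing items. C.5.d has care managers using eTUMS to track hospitalisation, pharmacy and laboratory status, which may mean only reading claims. The cost-effectiveness analysis is described as exploratory in C.5.j.

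Much of this stands, and it narrows the point. A reader might infer that capture does differ by arm, or that only CCM patients have care-manager entries. The documents support neither. Care managers recruit all patients before randomisation, automatic notices of major claims events carry no stated arm restriction, and nothing says whether EC patients receive routine care management from the insurer. A reader might also take all 22 scheduled CCM contacts in Table 4 (10 + 12) as medication reviews, but the weekly sessions deliver self-management modules.

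What the reply does not settle is the rule. The fills and tests in C.5.c are given as examples, while C.5.f names eTUMS itself as the concordance source. The Aim 3 paragraph describes a record review with an assessment tool, not a claims extract. CPT codes price a visit once it has been counted; they do not decide which visits are counted.

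**Conclusion.** The point holds as a weakness in outcome definition: capture of guideline concordance and of Aim 3 utilisation and costs can differ by arm, because the named source includes care-manager input that is likely to be concentrated in CCM and no rule keeps that input out of scoring. The three descriptions of the Aim 3 utilisation source also need reconciling, whatever the size of any bias.

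The size is unknown. The false-positive rates above rest on assumed capture differences, equal true concordance of 27.1%, the plan's ICC and cluster size, and a normal approximation. They should not be read as an estimate of bias in this trial. The 10-point case would be over half of the planned 19.4-point difference.

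A reader might infer that every secondary outcome, or the trial's main result, is compromised. It is not: the Aim 1 hospitalisation outcome is assigned to claims files, and productivity and the primary outcomes come from the patient survey. This is a worthwhile correction because it is cheap, not because harm has been shown.

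**What to change.** 1. Score guideline concordance, and Aim 3 inpatient, outpatient and ER utilisation and costs, only from the pharmacy, laboratory and medical claims fields, with identical code lists in both arms.
2. State that care-manager-entered eTUMS fields are excluded from outcome scoring and used only for fidelity and process description.
3. Reconcile C.5.c, Table 5 and the utilisation, quality-of-care and Aim 3 paragraphs of C.5.f to that source. Leave the survey outcomes and the claims-based hospitalisation outcome as they are.

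The cost is a few sentences and agreed code lists. The claims feeds are already held, and the sample size does not change. The downside is that services never billed to the plan are missed, but under the same rule in both arms. This also fits C.5.h, where the business case counts only utilisation costs within the plan.

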**Table 4: Mood Disorders CCM Core Elements: Life Goals Collaborative Care**

CCM Core Element 1: Life Goals Skills Management Enhancement	10 weekly 30-min telephonic sessions utilizing the web-based Life Goals program (52, 95) 
 
• Core modules cover management of depressive and manic symptoms
 
• Additional web modules utilized as clinically indicated (e.g., wellness, foods and moods, exercise, substance use, anxiety, psychosis, anger/irritability, metabolic risk)
 

CCM Core Element 2: Access / Continuity Parameters for Care Manager	12 monthly patient telephone contacts for 1 year (in addition to the skills management training above) to trouble-shoot self-management issues and summarize clinical status

	
Scheduled and Ad Hoc Clinical Assessments and Registry Data Utilization
 
 
• Ad hoc contacts at either care manager or participant initiation based on clinical or other concerns, including response to participants within one business day.
 
• “In-reach” to treating clinicians for hospitalization, ER visits, or specialty consultation
 
• Communication of clinical assessment data to mental health provider
 
• Collaboration with family as permitted
 
• Resource referral as needed
 

CCM Core Element 3: Provider Decision Support via Depression and Bipolar Disorder Clinical Practice Guidelines(96, 97)
	
Provider contacts; care manager elicits preference for mode of communication with provider (e.g., call, email, fax)
 
 
• Same content as clinic-based CCM
 
• Guidelines based on AHRQ depression in primary care and APA bipolar guidelines
 
• Will alert provider that his/her patient is receiving Life Goals and when he/she completes participation
 

The mood disorders CCM intervention (“Life Goals Collaborative Care”) consists of: (a) a web-based patient self-management skills enhancement (CCM-1), (b) enhanced information flow and continuity of care via a care manager (CCM-2), and (c) decision support, or situation-specific evidence-based clinical practice guideline recommendations for providers (CCM-3)- see Table 4 (98). The CCM will be implemented utilizing telephonic contact with patients and providers by the Aetna care managers who participated in the Aetna care management pilot study, based on a recommended caseload of 80-100 patients each (99). The care managers will also use the Life Goals web portal as a guide for each session.

Care managers will implement the three CCM Core Elements as follows:

**CCM-1: Web-based Self-Management Support:** The care manager will deliver the Life Goals Program adapted for mood disorders via telephone using a website that contains modules, exercises, and other information for patients and the CM (52, 95). The Life Goals program utilizes psychoeducation based on Social Cognitive Theory, emphasizing Motivational Interviewing and cognitive-behavioral techniques, particularly behavioral activation, to address symptom management and problem-solving skills. Ten core modules will be delivered over 10 weekly telephonic sessions of 30 minutes (59, 100) using content available from the Life Goals website. An additional six modules can be implemented based on patient preferences for other specific self-management topics (101), and will be tracked as part of the CCM engagement index (Section C.5.h). Both the CM and patients will also have access to additional exercises and tailored modules via the Life Goals web portal. For patients with bipolar disorder, at least one of the modules will focus on coping with manic symptoms, while patients with unipolar depression will also receive an additional module on depressive symptoms (100).

**CCM-2: Access/Continuity:** This core element consists of three components:

- **Patient Clinical Assessment:** During the first 10 weeks, each fourth call (monthly) will also include an assessment of overall clinical and treatment status (~15 minutes). Assessment will include the 9-item Patient Health Questionnaire (PHQ-9)(102, 103) to assess depressive symptoms, the 8-item Internal State Scale (ISS; (52, 104-106) to assess manic symptoms and well-being; medication use, adherence (7, 107), and side effects. The intake contact includes identification of care providers and recent contacts, and each follow-up call will include a focus on maintaining engagement/continuity. These calls will continue on a monthly basis for up to one year of participation, with additional phone contacts made to follow up in the event of a hospitalization or emergency room visit based on our RCTs (50-53, 108).
- **Claims Database/Registry Review:** The care manager will also use the eTUMS registry to track inpatient hospitalizations, pharmacy and laboratory status. These data, available in a clinically useful time frame (Section C.5.c), will assist the patient with trouble-shooting illness management, and assist the care manager in identifying opportunities for intervention or quality enhancement.
- **Provider communication:** Care management strategies to date have under-emphasized provider engagement (9). In the mood disorders CCM, the care manager will contact the provider at the time of patient enrollment to introduce the CCM and to determine how best to integrate CCM procedures into the provider’s practice needs. This initial contact will identify the optimal mode of communication between

provider and care manager, as well as delineation by the provider for the care manager of the expected care plan going forward (frequency of visits, medications, lab tests such as cardiometabolic monitoring). After this initial engagement and care planning contact, the care manager will contact the provider in the event of hospitalization, emergency room visit, or development of a new clinical issue, as well as to cue them if there is a crisis encounter (e.g., suicidality).

**CCM-3: Provider Decision Support:** As noted above, the care manager will have obtained clinical assessment data each month plus eTUMS-based data on pharmacy refills (weekly) and laboratory utilization (monthly). Using these multi-component assessment and treatment data, s/he will communicate situation-specific treatment options based on clinical practice guidelines for bipolar disorder (96, 98). For instance in the case of unipolar depression, non-response or partial response to medication (defined as <50% reduction in PHQ-9 score and PHQ-9  $\leq$ 9) would be followed by the care manager providing a series of treatment options based on current guidelines (97, 109). For those with bipolar disorder and presence of subtherapeutic lithium levels and manic symptoms, the care manager would also outline options based on clinical practice guidelines (110). It is important to note that, as in our prior studies (50-53, 108), the CCM is designed to supplement care and does not replace or control provider decision-making. That is: clinical decision-making remains in the hands of the provider. CCM therefore enhances care processes by: (a) enhancing patient skills to facilitate treatment participation, (b) offering the provider timely information, and (c) outlining situation-specific evidence-based treatment options.

**C.5.e. Implementation Procedures.** The study will be managed by the **Aetna Joint Operating Committee** led by Drs. [name] and Un and includes [name], PsyD, Aetna Clinical Specialty Programs Head, and [name], Aetna Head of Program Development (Section C.5.k, see support letter from [name]). We will implement the CCM using Enhanced REP (76, 77, 79). Our research implementation infrastructure will provide, keeping with the theme of “light footprint” of research, the customized **package** of CCM procedures (see Appendix), supported by 16 hours of **training** at study initiation, followed by ongoing **technical assistance**. CCM Fidelity monitoring will be incorporated into ongoing Aetna CM audits (Section C.5.c).

**Packaging** includes an implementation manual for all three CCM components developed by [name] as well as the secure web-based self-management program for care managers and patients for the CCM-1 component (52, 95).

**Training** for care managers will follow existing Aetna standard procedures for telephonic and web-based training. This will consist of 16 hours of telephonic training by [name] and her study team over 2 weeks modeled after our current on-site training package.

**Technical assistance** will be provided by the Joint Operating Committee and supported by study consultants [name] (telephonic care management) and [name] (implementation processes). Joint Operating Committee members will conduct conference calls with the care managers (weekly) and supervisors (monthly) to guide the use of CCM components, particularly with regard to interface issues between: care managers and patients; care manager and providers/practices; and patients and providers. The Joint Operating Committee will have separate quarterly and ad hoc calls with consultants for debriefing and advice.

**C.5.f. Data Collection and Measures.** Key outcomes data will be ascertained from patients (including surveys, medical record- eTUMS reviews, and claims data) and organizational surveys (Table 5).

**Patient survey:** A concise (15-30 minute) quantitative survey will be collected from patients via phone at baseline, 6, 12, 18, and 24 months thereafter by the research associate (RA). If the RA is unable to reach the patient via phone for follow-up assessments after multiple attempts, a survey will be mailed to the confirmed last known address of the participant as a final attempt to receive this data. Patients will be asked to return this survey without any identifying information on the survey or the envelope. The survey will contain a subject ID number to identify the patient’s survey when it is returned via mail. Patient outcomes data will be entered by the RA into a database on a password-protected research computer within a secure network server at the University of Michigan.

**Patient utilization and cost data,** described below will be ascertained from the Aetna eTUMS and claims databases, and exported securely for merging with survey data and analysis at the University of Michigan.

